TRADIPITANT
VP-VLY-686-3101

**A RANDOMIZED, DOUBLE-BLIND, PLACEBO-
CONTROLLED, EFFICACY STUDY OF THE NEUROKININ-1
RECEPTOR ANTAGONIST VLY-686 IN PATIENTS WITH
ATOPIC DERMATITIS**

Document Type: Clinical Study Protocol
Sponsor: Vanda Pharmaceuticals Inc.
[name]
[name]
[name]
USA
Study Product: tradipitant (VLY-686)
Protocol Number: VP-VLY-686-3101
Study Phase: III
IND Number: 122741
NCT Number: NCT03568331

Date: 12 August 2019

Status: Final

SYNOPSIS

Name of Sponsor/Company: Vanda Pharmaceuticals Inc.	
Name of Investigational Product: tradipitant (VLY-686)	
Title of Study: A Randomized, Double-Blind, Placebo-Controlled, Efficacy Study of the Neurokinin-1 Receptor Antagonist VLY-686 in Patients with Atopic Dermatitis	
Study center(s): Multicenter in North America	
Studied period: Date first patient enrolled: July 2018 Estimated study duration: 6 months	Phase of development: III
Number of patients (planned): Approximately 350 patients randomized (175 per arm, 1:1 randomization scheme), diagnosed with atopic dermatitis with treatment-resistant pruritus (i.e. pruritus duration of > 6 weeks despite the use of antihistamines or corticosteroids)	
Inclusion Criteria:	

1. Ability and acceptance to provide written informed consent; and sufficiently fluent in English to participate in the trial;2. Male and non-pregnant, non-lactating female patients aged 18 – 70 years (inclusive);
a. Note: Principal investigators are advised to enroll a patient population that reflects the demographics of the overarching United States population. Demographics in this context refer to age, sex, race, and ethnicity.3. Diagnosed with atopic dermatitis
a. $\geq 1\%$ body surface area (BSA) of AD involvement at the screening and baseline visits;b. Presence of excoriations at screening and baseline visits (i.e. SCORing Atopic Dermatitis index excoriation score > 0)c. Note: Principal investigators are advised to enroll a patient population that reflects the severity distribution of the overarching atopic dermatitis population seen in the United States population. Severity in this context refers to mild, moderate, and severe atopic dermatitis.4. Suffering from chronic pruritus with pruritus being actively present for at least 6 weeks prior to screening despite the use of antihistamines or corticosteroids;5. Worst Itch Numerical Rating Scale (WI-NRS) score ≥ 5 points at the screening and baseline visit;	

6. Daily diary reporting Worst Itch Numerical Rating Score (WI-NRS) average score for maximum itch severity ≥ 7 points between screening and baseline visits;
 - a. *Note: WI-NRS average score for maximum itch severity will be determined based on the average of the 50% worst daily NRS scores for maximum itch severity (the daily scores ranging from 0 to 10) during the screening period (between visits 1 and 2). A minimum diary compliance of 70% during the screening phase (between Visits 1 and 2) is required before randomization. For patients who do not have at least 70% diary compliance preceding the planned randomization date, randomization should be postponed until this requirement is met, but without exceeding the 45-day maximum duration for screening.*
7. Patients with Body Mass Index (BMI) of ≥ 18 and ≤ 40 kg/m^2 ($\text{BMI} = \text{weight} (\text{kg}) / [\text{height} (\text{m})]^2$);
8. Patients must agree to the following study restrictions:
 - a. Males of procreative capacity (not surgically sterile) will use an acceptable method of contraception from randomization through 1 month following the last dose of study medication. Examples of acceptable contraception for males include abstinence, use of a barrier method, or surgically-sterilized or post-menopausal partner.
 - b. Females of child-bearing potential (not surgically sterile or post-menopausal, defined as 12 months with no menses without a medical cause) will use an acceptable method of contraception from the earlier of screening or 1 month prior to randomization through 1 month after the last dose of study medication. Examples of acceptable methods of contraception for females include abstinence, the use of 2 independent barrier methods, hormonal contraception plus 1 barrier method, or surgically sterilized partner.
9. Willing and able to comply with all study requirements and restrictions;
10. Willing to not participate in any other interventional trial for the duration of their participation;
11. Patients must be in good health as determined by past medical history, physical examination, electrocardiogram, clinical laboratory tests, and vital signs.

Exclusion Criteria:

1. Chronic pruritus due to condition other than atopic dermatitis (AD);
2. Superinfection of AD;
3. Unwilling or unable to follow medication restrictions described in [Section 7.2](#), or unwilling or unable to sufficiently washout from use of restricted medication.
4. Under medical treatment for a skin disease with a therapy listed in the prohibited medications section in [Table 3](#) that may influence the results of the study;
5. Have been treated with the following therapies:

- a. An investigational drug, including placebo, within 8 weeks or within 5 half-lives (if-known), whichever is longer, prior to the baseline visit or
- b. A biologic for less than 5 half-lives (if known) or 16 weeks prior to the baseline visit
- 6. Recent history (within six months of screening) of drug or alcohol abuse as defined in DSM-5 Diagnostic Criteria for Drug and Alcohol Abuse and/or a positive drug or alcohol screen at the Screening visit and Baseline;
- 7. Patient has ever made a suicide attempt and/or had suicidal ideation of type 4 or 5 on the Columbia-Suicide Severity Rating Scale (C-SSRS) or patient is at risk of suicide at Screening or Baseline, in the opinion of the Investigator;
- 8. Any medical procedure requiring general anesthetic within three months of the Baseline Visit or any procedure requiring sedation within one month of the baseline visit;
- 9. Current clinically significant cardiovascular, respiratory, neurologic, hepatic, hematopoietic, renal, gastrointestinal or metabolic dysfunction unless currently controlled and stable, including (but not limited to) the following:
 - a. Uncontrolled diabetes mellitus defined as HbA1c >7%;
 - b. Positive hepatitis C antibody test (anti-HCF);
 - c. Positive hepatitis B surface antigen (HBsAg);
- 10. History (including family history) or current evidence of congenital long QT syndrome or known acquired QT interval prolongation;
- 11. History of intolerance and/or hypersensitivity to medications similar to tradipitant and its accompanying excipients;
- 12. Indication of impaired liver function (values for AST, ALT, or bilirubin > 2 times the Upper Limit of Normal (ULN));
- 13. Has a creatinine level > 1.25x ULN
- 14. Anyone affiliated with the site or sponsor and/or anyone who may consent under duress;
- 15. Any other sound medical reason as determined by the Investigator including any condition which may lead to an unfavorable risk-benefit of study participation, may interfere with study compliance or may confound study results.

Investigational product, dosage and mode of administration:

A single oral capsule of tradipitant 85 mg or matching placebo will be orally administered twice daily for a total daily dose of 170 mg.

Duration of treatment (Randomization Phase): 8 weeks

Reference therapy, dosage and mode of administration:

Placebo capsules will be provided in size and appearance identical to those containing VLY-686 and will be administered orally.

Objectives:**Primary Objective:**

- To evaluate the efficacy of VLY-686 in reducing worst itch in patients with chronic pruritus in atopic dermatitis as measured by Worst Itch Numerical Rating Scale (WI-NRS) at Week 8.

Secondary Objectives:

- To evaluate the efficacy of VLY-686 in improving disease severity in patients with atopic dermatitis as measured by the validated Investigator Global Assessment scale for Atopic Dermatitis (vIGA-AD).
- To evaluate the efficacy of VLY-686 in improving disease severity in patients with atopic dermatitis as measured by the SCORing Atopic Dermatitis (SCORAD) index and Eczema Area and Severity Index (EASI).
- To evaluate the proportion of patients with improvement of WI-NRS \geq 4-point reduction.
- To evaluate the proportion of patients with improvement on SCORAD index of at least 50%, 75% or 90% improvement.
- To evaluate the proportion of patients with improvement on the EASI of at least 50%, 75% or 90% improvement.
- To assess the efficacy of tradipitant on global measures of improvement as measured by Clinical Global Impression of Change (CGI-C) and Patient Global Impression of Change (PGI-C).
- To assess the efficacy of tradipitant on quality of life as measured by the Patient Oriented Eczema Measure (POEM), Dermatology Life Quality Index (DLQI), Healthly Days Core Module (4 questions) (HRQOL-4), Insomnia Symptom Questionnaire (ISQ) and Patient Benefit Index - Pruritus (PBI-P).
- To explore the safety and tolerability of multiple oral doses of VLY-686.

Pharmacogenomic Sub-Study:

- Identify genetic markers that correlate with response to tradipitant treatment.
- Identify genetic markers that correlate with adverse events that may occur upon treatment with tradipitant.
- To identify genetic markers that are associated with atopic dermatitis and/or pruritus and disorders/diseases associated with NK-1 receptors.
- To identify genetic markers that are associated in the metabolism, distribution, and/or excretion of tradipitant and its metabolites.

Overall Design:

This is multicenter, randomized, double-blind, placebo-controlled study to be conducted in the United States. Approximately Three Hundred and Fifty (350) patients diagnosed with atopic dermatitis, who satisfy the selection criteria for the study, will be randomized to receive either tradipitant 85 mg or matching placebo BID.

The study is divided into two phases: the pre-treatment phase and the evaluation phase. The pre-treatment phase includes a screening and a baseline visit where patients' eligibility for the study will be assessed. Washout of medications will occur during the screening phase.

The evaluation phase includes 8 weeks of randomized, double-blind, placebo-controlled treatment. In-clinic evaluations will occur at Screening, Baseline, and Weeks 2, 4, 6, and 8.

Criteria for evaluation:

Efficacy:

Efficacy assessments will include:

- Worst Itch Numerical Rating Scale (WI-NRS)
- SCORing Atopic Dermatitis (SCORAD) index
- Validated Investigator Global Assessment scale for Atopic Dermatitis (vIGA-AD)
- Eczema Area and Severity Index (EASI)
- Clinical Global Impression of Change (CGI-C)
- Patient Global Impression of Change (PGI-C)
- Patient Oriented Eczema Measure (POEM)
- Dermatology Life Quality Index (DLQI)
- Patient Benefit Index – Pruritus (PBI-P)
- Insomnia Symptom Questionnaire (ISQ)
- Healthly Days Core Module (4 questions) (HRQOL-4)

Safety:

- Safety and tolerability assessments will include the recording of adverse events (AEs), physical examinations, clinical laboratory evaluations, vital signs, and electrocardiograms.
- The Columbia-Suicide Severity Scale (C-SSRS) will be used to assess suicidal behavior and ideation.

Table 1: Schedule of Evaluations

Phase	Pre-Treatment		Evaluation			
	V1 Screening	V2 Baseline	V3	V4	V5	V6
Visit	Up to Day -45	Day 0	Day 14 ¹	Day 28 ¹	Day 42 ¹	Day 56 ¹ or ET
Study Day						
Informed Consent Form (ICF) ²	X					
Eligibility assessment	X	X				
Patient demography	X					
Medical history	X					
Prior/concomitant medications	X	X	X	X	X	X
Adverse Event (AE) Assessment ³	X	X	X	X	X	X
Serum β-HCG (for WOCBP)	X					X
Urine pregnancy test (for WOCBP)		X	X	X	X	
HbA1c	X					
Hepatitis B/C screen	X					
Drug and alcohol screen	X	X	X	X	X	X
Hematology, chemistry, and urinalysis	X	X		X		X
IgE collection	X	X	X	X	X	X
Cytokine Panel ⁴	X					X
Filaggrin Analysis	X					X ⁵
Pharmacogenetic (PG) sample	X					X ⁵
Pharmacokinetic (PK) sample		X	X	X	X	X
Resting 12-lead ECG	X	X	X	X	X	X
Vital signs and body measurements ⁶	X	X	X	X	X	X
Physical Examination (PE) ⁷	X	X	X	X	X	X
Columbia-Suicide Severity Rating Scale (C-SSRS) ⁸	X	X	X	X	X	X
Medical History of Pruritus Questionnaire		X				
Medical History of Atopy Questionnaire	X					
Pruritus Assessment (incl. NRS, VRS)	X	X	X	X	X	X
SCORing Atopic Dermatitis (SCORAD) index	X	X	X	X	X	X
Eczema Area and Severity Index (EASI)	X	X	X	X	X	X

Phase	Pre-Treatment		Evaluation			
	V1 Screening	V2 Baseline	V3	V4	V5	V6
Visit	Up to Day -45	Day 0	Day 14 ¹	Day 28 ¹	Day 42 ¹	Day 56 ¹ or ET
Study Day						
Validated Investigator Global Assessment scale for Atopic Dermatitis (vIGA-AD)	X	X	X	X	X	X
Patient Benefit Index – Pruritus (PBI-P) ⁹		X	X	X	X	X
Patient Global Impression of Change (PGI-C)			X	X	X	X
Clinical Global Impression of Change (CGI-C)			X	X	X	X
Patient Oriented Eczema Measure (POEM)	X	X		X		X
Dermatology Life Quality Index (DLQI)	X	X	X	X	X	X
Insomnia Symptom Questionnaire (ISQ)	X	X		X		X
Healthy Days Core Module (4 questions) (HRQOL-4)	X	X		X		X
Daily Diary	↔					
Photography		X		X		X
Randomization		X				
Study medication dispensation ¹⁰		X	X	X	X	
Study medication collection & compliance			X	X	X	X
Daily diary distribution and instruction	X					
Patient daily diary review		X	X	X	X	X

1 within +/- 3 days

2 Informed Consent will be obtained prior to performance of any study procedure(s)

3 Adverse Event collection will begin at the time the ICF is signed

4 If V1 cytokine panel sample is missed, sample should be drawn at the next in-clinic visit.

5 Sample collected at V1. Sample collected at V6/EOS only if randomized under Protocol Amendment 1 and sample was not already collected at V2.

6 Body height will only be collected at screening (V1), body weight will be collected at visits 1, 2, and 6.

7 An abbreviated physical examination will be performed at V2 (Baseline) and post-baseline visits 3-5 ONLY if clinically indicated.

- 8 The Screening/Baseline C-SSRS will occur at V1 (Screening). The Since Last Visit C-SSRS will occur at all other visits.
- 9 At V2 (Baseline), the Patient Needs Questionnaire (PBI-P(PNQ)) will be administered. The Patient Benefits Questionnaire (PBI-P(PBQ)) will be administered at subsequent visits.
- 10 Patients will be instructed to take their first dose of study medication on the evening of Day 0.

ET = Early Termination; WOCBP = Women of Child-bearing Potential; ECG = electrocardiogram; C-SSRS = Columbia Suicide Severity Rating Scale; NRS = Numeric Rating Scale; VRS = Verbal Response Scale; HbA1c= Haemoglobin A1c or glycated haemoglobin; IgE= Immunoglobulin E

1. STATISTICS

1.1. Sample Size and Accrual

To detect a 1.2 point treatment difference in worst itch score, as measured by NRS, between VLY-686 and placebo with a standard deviation (SD) of 3, a sample size of 175 patients per arm (total 350 patients) provides approximately 96% power based on a two-sided Student's T-Test with a 5% significance level. In addition, a total sample size of 350 patients (175 per arm) will also provide approximately 91% power to detect a 18% response difference, according to 35% and 53% response rates on placebo and VLY-686 respectively in the phase II study, based on a two-sided Fisher's Exact Test with a 5% significance level.

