1.2.1. General

Statistical analyses will be performed using two-sided tests.

Data will be summarized by treatment group (and by visit when applicable), with respect to demographic and baseline characteristics, efficacy variables, and safety variables.

Summary statistics will include the mean, N, standard deviation, median, minimum, and maximum values for continuous variables, and frequencies and percentages for categorical variables.

For the analyses of change from baseline, only patients with a baseline and at least one (1) post-baseline measure will be included in the analysis. Unless otherwise specified, baseline is defined as the latest non-missing observation across all the visits in the screening phase, before the active study drug begins. Endpoint will be the latest non-missing observation across all the post-baseline visits in the evaluation phase.

Low enrolling sites will be pooled for analysis and the pooling algorithm will be determined prior to breaking the blind. The goal of pooling low enrolling sites is to have a sufficient number of patients per treatment group within a site for the analysis models and for the evaluation of the treatment-by-site interaction for the primary endpoint. Unless otherwise specified, the pooled sites will only be used in the analyses where the site has an effect. The actual sites rather than the pooled sites will be specified in the data listings.

Details of the model and the analyses will be specified in the SAP. All statistical analyses will be performed using SAS®, Version 9.1.3 or higher.

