1.2.2. Patient Populations for Analysis

The following analysis populations will be defined for this study:

Intent-to-Treat: will include any patient randomized into the study that receives a dose of study drug and that has completed at least one post-baseline efficacy measurement while on study medication;

Safety: Any patient randomized into the study that receives a dose of study drug;

Per-Protocol: Any patient who is randomized and receives the protocol required study drug exposure and required protocol processing.

Efficacy analyses will be performed on the Intent-to-Treat population and the Per-Protocol population. Safety summaries will be based on Safety set. Patient characteristics will be presented for all patients randomized.

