1.2.3. Patient Disposition

Study completion and reasons for discontinuation for all randomized patients in the double-blind phase will be summarized for each treatment group. Discontinuations by reason will be tabulated by visit for each treatment group.

Time to discontinuation due to adverse events, lack of efficacy and for any reason will be analyzed using Kaplan-Meier survival techniques; the log-rank test will be used for group comparison.

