1.3.2. Secondary Efficacy Analysis

The secondary efficacy outcomes include:

- DDSS
- Itch questionnaires including diary WI-NRS, site WI-NRS and VRS
- Proportion of patients with improvement of WI-NRS \geq 4-point reduction;

- SCORAD;
- EASI;
- Proportion of patients with improvement on SCORAD index of at least 50%, 75% or 90% improvement.
- Proportion of patients with improvement on the EASI of at least 50%, 75% or 90% improvement.
- vIGA-AD;
- PGI-C;
- CGI-C;
- PBI-P;
- HRQOL-4;
- POEM;
- DLQI;
- ISQ;
- Pharmacokinetic-Pharmacodynamic correlation.

Continuous endpoints will be summarized and analyzed in a similar manner as the primary endpoint. Categorical endpoints will be analyzed by a Cochran–Mantel–Haenszel (CMH) test. Details of the analysis will be described in the SAP.

Time to event data will be analyzed using the Kaplan-Meier method, and the treatment group differences will be tested by the log-rank test. Details of the analysis will be described in the SAP.

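### Does the sample size need a drop-out allowance, given that power is quoted at the full number randomised?

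*SAP*

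**What the plan says.** The protocol synopsis plans "Approximately 350 patients randomized (175 per arm, 1:1 randomization scheme".

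SAP Section 1.1 uses the same 175 per arm for both power statements:

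- **Primary.** "To detect a 1.2 point treatment difference in worst itch score, as measured by NRS", with an SD of 3 and a two-sided 5% t-test, "a sample size of 175 patients per arm (total 350 patients) provides approximately 96% power".
- **Responder.** "a total sample size of 350 patients (175 per arm) will also provide approximately 91% power to detect a 18% response difference", from phase II rates of 35% and 53%, by a two-sided 5% Fisher's exact test.

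The section gives no loss rate, number evaluable or inflation factor. Four other places in the SAP bear on the point:

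- Section 1.2.1 (General): "Endpoint will be the latest non-missing observation across all the post-baseline visits in the evaluation phase".
- Section 1.2.2 limits the efficacy population to dosed patients and requires of each patient "that has completed at least one post-baseline efficacy measurement while on study medication".
- Section 1.2.3 (Patient Disposition): "Time to discontinuation due to adverse events, lack of efficacy and for any reason will be analyzed".
- Section 1.3.2: "Categorical endpoints will be analyzed by a Cochran–Mantel–Haenszel (CMH) test". The details are left to a fuller SAP.

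Section 1.3.1 makes MMRM the primary method.

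**The concern.** A power figure computed at the number randomised holds only if every randomised patient contributes as assumed. This plan tabulates discontinuations, schedules an early-termination visit, and removes from the efficacy population anyone with no dose or no on-treatment efficacy measurement. Some loss is therefore foreseen, yet Section 1.1 is silent on it.

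The responder statement has two further weak points. Its power is for Fisher's exact test, which is not the planned test. The text also does not say how a patient without a Week 8 result is classified. If drop-outs count as non-responders, both response rates shrink and so does their difference.

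At stake would be a trial with less power than its planners believed, mainly for the responder comparison, which has the smaller margin.

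**Working it through.** **Inputs.** From SAP Section 1.1: difference 1.2, SD 3, rates 0.35 and 0.53, two-sided 5%, n = 175 per arm. The loss rate L is my assumption (5% to 20%), because the documents give none. CMH is computed as a single stratum, because no strata are named.

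**Step 1: reproduce the stated figures.**

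For the t-test, the noncentrality is 1.2 / (3 × √(2/175)) = 3.742 on 348 degrees of freedom, with critical value 1.967. Power is 96.2%, against about 96% stated.

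For the responder comparison, power is the sum of the two binomial probabilities over all tables that the test rejects. Fisher's exact test gives 90.7%, against about 91% stated. For CMH, a table with x responders of n in one arm and t responders in total is rejected when

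(x − t/2)² / [n² t (N − t) / (N² (N − 1))] > 3.84, with N = 2n.

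This gives 92.4% at 175 per arm. The planned test is thus slightly more powerful than the one quoted, and that mismatch alone makes the stated 91% conservative.

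**Step 2: primary comparison with loss.** The number analysed is 175 × (1 − L), rounded, and everyone lost is assumed to contribute nothing.

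| Loss | n per arm | t-test power |
|---|---|---|
| 5% | 166 | 95.3% |
| 10% | 158 | 94.3% |
| 15% | 149 | 93.1% |
| 20% | 140 | 91.5% |

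MMRM uses the visits that early leavers did attend. With four post-baseline visits, SD 3, drop-out split equally after Weeks 2, 4 and 6, and within-patient correlation 0.5 to 0.8 (compound symmetry or AR(1)), power for the Week 8 contrast is 94.5–95.6% at 10% loss and 92.2–94.9% at 20%.

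**Step 3: responder comparison with loss, CMH test.** There are three ways to treat a drop-out:

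- (a) Excluded: n falls as in step 2 and the rates stay at 0.35 and 0.53.
- (b) Last observation used: n stays at 175. If early leavers respond at half the usual rates (my assumption), both rates are multiplied by 1 − L/2. At 20% loss they become 0.35 × 0.90 = 0.315 and 0.53 × 0.90 = 0.477.
- (c) Counted as non-responders: n stays at 175 and both rates are multiplied by 1 − L. At 20% loss they become 0.35 × 0.80 = 0.280 and 0.53 × 0.80 = 0.424.

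| Loss | (a) Excluded | (b) Last observation, half rates | (c) Non-responders |
|---|---|---|---|
| 5% | 91.8% | 91.2% | 90.1% |
| 10% | 89.7% | 90.1% | 87.7% |
| 15% | 88.9% | 88.9% | 84.7% |
| 20% | 85.8% | 87.7% | 80.9% |

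Under (b), if early leavers respond at the usual rates, power stays at 92.4%. Column (c) applies only if 35% and 53% were rates among completers, which Section 1.1 does not say. If phase II already counted drop-outs as non-responders, (c) discounts twice. The steps in (a) are uneven because the test is discrete.

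**The case for a change.** The best case for a change is that Section 1.1 chose to quote responder power, so the figure should describe the planned analysis under realistic follow-up. As written, a reader cannot tell whether 91% should be read as 92% or as 81%. The spread comes from three things left unsaid: the expected loss, the handling of missing responders, and the basis of the phase II rates. Using CMH above is also generous. With Fisher's test, which Section 1.1 names, 10–20% loss gives 87.5–82.9% with drop-outs excluded, or 85.4–77.8% with drop-outs as non-responders. Correcting this would take a few words and no patients.

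The omission is real and the arithmetic is right, so that much stands. It carries less weight than it first appears to, for three reasons.

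- The figures below 80% belong to Fisher's test, which is not the planned analysis.
- The low end joins a high assumed loss to the harshest convention and to an unconfirmed reading of the phase II rates. The only general endpoint rule in the text, the last-observation definition in Section 1.2.1, points to column (b) instead, although the text does not say that it governs responders.
- The classification of missing responders is an analysis detail of the kind that Section 1.3.2 leaves to the fuller SAP. Its absence from a sample-size paragraph does not show that it is undecided.

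**Conclusion.** No change is needed. Section 1.1 states correct powers for the tests, effects and numbers that it names. It does not present them as powers after attrition.

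The primary comparison has room to spare: 132 per arm would give 90% power, so 175 can absorb the complete loss of 43 patients per arm (about 25%) before power falls below that level. The responder comparison is a supporting calculation. Under the planned test it stays between about 86% and 90% at 10–20% loss if drop-outs are excluded or their last observation is used on the half-rate assumption. It stays just above 80% in the harshest case computed.

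These results rest on an assumed loss of at most 20%, an unstratified CMH test, and the effect sizes in Section 1.1. At 5% loss the stated figures hold approximately under every convention: 95.3% for the primary and 90.1–91.8% for the responder comparison.

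Writing down a loss rate and re-quoting power for CMH would be a courtesy to the reader. The 350 patients, the tests, the endpoints and the reading of the results would all stay as they are, so this is a gap in description that costs the trial nothing.
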